#### **9.5. Rescue Therapy**

Frequency and percentage of subjects who received rescue therapy will be summarized. Subjects who received rescue therapy will be listed.

#### **9.6. Electrocardiogram (EKG)**

Any worsening from normal/not clinically significant abnormality at baseline to clinically significant abnormality will be summarized by actual treatment received and analysis visit. Subjects with clinically significant abnormality will be listed.

#### **9.7. Vital Signs**

Blood pressures and pulse rate, and changes from baseline will be summarized by actual treatment received and analysis visit.

#### **9.8. Laboratory Assessments**

For each type of laboratory assessments (chemistry, hematology, or urinalysis), any worsening from normal/not clinically significant abnormality at baseline to clinically significant abnormality will be summarized by actual treatment received and analysis visit. Subjects with clinically significant abnormality will be listed.

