16.2. General Considerations

All study parameters will be listed and a selected list of parameters will be summarized descriptively by treatment arm. The descriptive statistics will include number of observations (n), mean, standard deviation, minimum, and maximum for continuous parameter and frequency (n) and percent (%) for categorical parameters.

Details about the statistical analyses for this study will be provided in the statistical analysis plan (SAP).

All data manipulations and descriptive summaries will be implemented using SAS[®], Version 9.1.3 or later.

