16.7. Safety Analysis

All safety outcome measures will be summarized descriptively for the Safety Population. The safety outcome measures include adverse events (AEs), BCVA, slit-lamp biomicroscopy, indirect ophthalmoscopy, intraocular pressure (IOP), serum chemistry, hematology, urinalysis, vital signs, physical examination, fundus photography, fluorescein angiography, EKG and pregnancy.

AEs will be coded using the Medical Dictionary for Regulatory Activities (MedDRA).

Subjects with any AEs will be tabulated by system organ classification and preferred term specified in the MedDRA. Similarly, subjects with any ocular and non-ocular AEs and ESIs will be tabulated separately. AEs, ocular and non-ocular, as well as ESIs will also be summarized by relationship to treatment and maximum severity. In addition, SAEs and discontinuations due to AEs will be summarized.

Ocular safety outcome measures will be summarized using descriptive statistics.

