23.4.16. Hematology, Chemistry and Urinalysis

Approximately 10 mL of fasting blood and urine samples will be obtained at Visit 0/Screening (Day -14 to Day -1), Visit 4 (Week 4), Visit 6 (Week 12), Visit 11 (Week 24) and Visit 13/Exit (Week 32). The subjects will be asked to fast for a minimum of 8 hours prior to each blood and urine collection. Samples will be sent to a central laboratory for analysis.

There will be up to approximately 5 blood draws for immunogenicity. Approximately 10 mL or 2 teaspoons will be collected for each blood draw. The total amount of blood collected from each subject during this study will be up to approximately 50 mL.

Serum Chemistry, Hematology

The following is a list of the minimum parameters that will be measured. Other additional parameters may also be reported.

Chemistry	Hematology
Albumin	red blood cells (RBC)
Creatinine	white blood cells (WBC)
lactate dehydrogenase (LDH)	differential WBC
glucose	platelets (PLT)
calcium	hemoglobin (HGB)
potassium	hematocrit (HCT)
sodium	mean corpuscular volume (MCV)
cholesterol (total, HDL and LDL)	mean corpuscular hemoglobin (MCH)
triglycerides	mean corpuscular hemoglobin conc. (MCHC)
urea nitrogen	
bilirubin (total, direct, indirect)	
alkaline phosphatase (ALP)	
alanine aminotransferase (ALT)	
aspartate aminotransferase (AST)	
gamma glutamyl transferase (GGT)	
Human chorionic gonadotropin (hCG)*	

Prior to enrolling a subject, the Clinical Investigator will indicate on the source document if any screening laboratory values exclude the subject from participating in the study (e.g., serum creatinine > 1.3 mg/dL).

*Conduct only at Visit 0/Screening (Day -14 to Day -1), Visit 11 (Week 24) and Visit 13/Exit (Week 32).

Urinalysis

The following is a list of the minimum urine parameters that will be measured. Other additional urine parameters may also be reported.

Urinalysis
PH
Protein
Erythrocytes
Ketones
Glucose

Prior to enrolling a subject, the Clinical Investigator will indicate on the source document if any screening laboratory values exclude the subject from participating in the study.

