**Table 5: Safety Measures (Continued)**

Safety Measure	Note
Ophthalmoscopy findings: cup/disc ratio retina macula choroid vitreous	Indirect ophthalmoscopy will be performed prior to Lucentis ® injection and within 30 minutes after DE-122 or Sham injection, and any post IVT injection of rescue treatment.  Cup/disc ratio will be recorded with two decimal points (e.g., 0.80).  The retina, macula and choroid will be graded as either normal or abnormal.  Vitreous haze and opacification will be graded as: 0 = Clear Trace or 0.5+ = Trace 1+ = Few opacities, mild blurring 2+ = Significant blurring but still visible 3+ = Optic nerve visible, no vessels seen 4+ = Dense opacity obscures the optic nerve head.
Laboratory test: urinalysis hematology serum chemistry	Laboratory test results will be graded as: 1 = Normal 2 = Not Clinically Significant Abnormality 3 = Clinically Significant Abnormality 4 = No Results/Invalid Results 5 = Sample Not Collected  Refer to Section 23.4.16 of the protocol for the list of the minimum blood parameters and urine parameters.
Vital signs: systolic blood pressure diastolic blood pressure heart rate	Systolic blood pressure and diastolic blood pressure will be measured in mmHg. Heart rate will be measured by beats/minute. The average of two or three readings will be used.

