**Table 5: Safety Measures (Continued)**

Safety Measure	Note
EKG	
EKG report will be reviewed by the Clinical Investigator and will be graded as:
 
1 = Normal            2 = Abnormal, Clinically Insignificant            3 = Abnormal, Potentially Clinically Insignificant            4 = Abnormal, Potentially Clinically Significant            5 = Abnormal, Potentially Exclusionary            6 = Abnormal, Clinically Significant            7 = Unable to Evaluate            8 = Unable to evaluate but measurements provided are correct

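### SAP 9.8 specifies no per-analyte summary of laboratory values, changes from baseline or reference-range shifts, so changes below the clinically significant grade are not shown by arm

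*SAP*

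**What the plan says.** SAP 9.8 covers "For each type of laboratory assessments (chemistry, hematology, or urinalysis), any worsening from normal/not clinically significant abnormality at baseline to clinically significant abnormality", summarised by actual treatment and analysis visit. It adds one listing: "Subjects with clinically significant abnormality will be listed". Nothing else is specified for laboratory data.

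SAP Table 5 defines the measure behind that summary: "Laboratory test results will be graded as: 1 = Normal 2 = Not Clinically Significant Abnormality 3 = Clinically Significant Abnormality", followed by two codes for missing or invalid samples. The row gives no numeric value, unit, reference range or rule for clinical significance. For the analyte list it points to Protocol 23.4.16.

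Protocol 23.4.16 names the analytes, including haemoglobin, platelets, white cells, ALT, AST, GGT, alkaline phosphatase and bilirubin. It schedules samples at screening and Weeks 4, 12, 24 and 32, and states: "Samples will be sent to a central laboratory for analysis".

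Protocol 16.7 says "All safety outcome measures will be summarized descriptively for the Safety Population" and includes serum chemistry, hematology and urinalysis among those measures. Protocol 16.2 gives the general rule for summaries: n with "mean, standard deviation, minimum, and maximum for continuous parameter", and frequency and percent for categorical ones. SAP 6 has a similar rule.

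**The concern.** Safety is part of the primary objective and the study tests no hypothesis, so descriptive tables are the safety evidence. The protocol treats these analytes as relevant enough to set numeric haemoglobin, platelet, white-cell and liver limits at entry (Protocol 8.2).

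The plan nevertheless counts only subjects who reach the top laboratory grade. A move from normal to abnormal but not clinically significant is not counted, and neither is a general drift within the normal range. The summary is organised by type of test, so as described it need not separate a fall in haemoglobin from a change in white cells.

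With arms of 17, 31 and 28, counts of rare threshold crossings carry little information. A mean change uses every subject. A moderate shift on DE-122 could leave the 9.8 table empty or nearly so.

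**Working it through.** The plan states no figure on this point, so there is none to reproduce. The check has two parts.

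**1. What the SAP specifies for each numeric safety measure**

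| Measure | SAP section | Values summarised | Change from baseline summarised |
|---|---|---|---|
| Cup/disc ratio | 9.3 | yes | yes |
| IOP | 9.4 | yes | yes |
| Vital signs | 9.7 | yes | yes |
| Chemistry, hematology, urinalysis | 9.8 | not specified | not specified; only the shift to clinically significant |

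The general rule in SAP 6 does not clearly close the gap. It gives mean and SD for continuous variables, but Table 5 makes the laboratory measure a category. A programmer working from 9.8 and Table 5 would produce a grade-shift count.

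**2. Illustration of size**

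Inputs from the documents: 28 subjects in the 4.0 mg arm, 31 in the 2.0 mg arm, 17 in the control arm.

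Assumed inputs (the documents give no laboratory means, SDs or significance thresholds): baseline haemoglobin normal with mean 13.5 and SD 1.2 g/dL, restricted to at least 10 at entry; change from baseline normal with SD 0.8; true mean fall 0.7; a result is called clinically significant when it is below a threshold T. All values below T are counted.

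Let p = P(baseline + change < T). The chance that the table shows no case among n subjects at one visit is (1 − p)^n.

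| T (g/dL) | p | Expected cases, n = 28 | Chance of none, n = 28 |
|---|---|---|---|
| 10 | 2.5% | 0.7 | 50% |
| 10.5 | 5.4% | 1.5 | 21% |
| 11 | 10.4% | 2.9 | 5% |

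With T = 10 and the fall varied over 0.5, 0.7 and 1.0 g/dL, p is 1.7%, 2.5% and 4.0%, and the chance of none among 28 is 61%, 50% and 32%. If both DE-122 arms (31 + 28 = 59) had the 0.7 fall, the chance of none in either at T = 10 is 23%.

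For comparison, the precision of a difference in mean change, 28 versus 17:

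half-width = t(0.975, 43) × SD × √(1/17 + 1/28) = 2.017 × 0.8 × 0.3075 = 0.50 g/dL.

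For a change SD of 0.6 the half-width is 0.37, and for 1.2 it is 0.74. A 0.7 fall therefore exceeds the half-width at SD 0.8 but not at SD 1.2. At SD 0.8 the interval would exclude zero about 79% of the time for a true fall of 0.7, and about 51% for 0.5.

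A version without haemoglobin-specific inputs gives a similar picture. If an analyte is normal with SD 1, a true shift of 0.5 SD occurs and results beyond 2, 2.5 or 3 SD are called clinically significant, the chance of no case among 31 is 12%, 49% or 82%. With a 1 SD shift it is under 1%, 12% or 49%.

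**The case against.** - **A reader might infer that a laboratory effect would appear in no planned summary.** The documents do not support that. Clinically significant worsening is tabulated by arm and visit in 9.8. A laboratory finding with clinical significance can be an adverse event (Protocol 12.1.1), and those are tabulated by preferred term (SAP 9.1), which would separate haemoglobin from white cells. This stands, but both routes need clinical significance, so smaller shifts pass through neither.
- **A reader might infer that the SAP breaches the protocol.** That is not clear. Protocol 16.2 says a selected list of parameters is summarised, leaves detail to the SAP, and accepts counts and percentages for categorical data. Protocol 16.2 also promises that all parameters are listed. The grade-shift count is thin but is a descriptive summary; a listing is not a summary by arm.
- **A reader might infer that the grade is the investigator's personal judgement.** Table 5 names no grader for laboratory results. For EKG it does: "EKG report will be reviewed by the Clinical Investigator and will be graded as".
- **Panel-level grading is one reading.** Table 5 says "Laboratory test results will be graded as", which may mean analyte by analyte, with test type only organising the output. The level is left open.
- **A reader might infer that bleeding is a stated systemic risk that depends on this table.** Protocol 7.1.1 anticipates no systemic toxicity. Protocol 12.1.3 says no data link DE-122 to telangiectasia or bleeding, and makes those events of special interest, tabulated in their own right.
- **The haemoglobin figures rest on assumed inputs.** The 10 g/dL value is an example in an entry exclusion, not a significance threshold, and the answer is sensitive to it. This stands, which is why the threshold is varied above.

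**Conclusion.** The gap is real: the SAP specifies no laboratory summary by analyte of value, change from baseline or range shift, and treats laboratory data more coarsely than its other numeric safety measures. The consequence is limited to changes that stay below the clinically significant grade.

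How much is lost depends on where that grade is set, which the documents do not say. Under the haemoglobin assumptions, a 0.7 g/dL fall leaves the 4.0 mg row empty at a given visit with a chance of 50% at a threshold of 10 g/dL and 5% at 11. A large effect or a low threshold would show in the planned table. These figures cover one analyte, arm and visit, while there are four post-baseline laboratory visits; they illustrate and do not estimate. The case for change rests on the comparison of sections, not on them. The change should be made, as an improvement to the analysis rather than a correction of a protocol breach.

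**What to change.** In SAP 9.8:

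1. For each numeric chemistry and hematology analyte in Protocol 23.4.16, summarise n, mean, SD, minimum and maximum of the value and of the change from baseline, by actual treatment and analysis visit.
2. Add low/normal/high shift tables from baseline for the same analytes, using the central laboratory's reference ranges.
3. Keep the shift to clinically significant, but tabulate it by analyte, including each urinalysis parameter.
4. In Table 5, state who assigns the laboratory grade and whether it is assigned per analyte or per test type.

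The laboratory results are already collected, so no new assessment is needed. The cost is programming standard tables and more output pages.

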## 10. PHARMACOKINETIC ANALYSES

All PK analyses will be performed on the PK population, with subjects as treated. Pharmacokinetic parameters (AUC,  $C_{max}$ ,  $t_{max}$ , and  $t_{1/2}$ ) will be summarized descriptively by actual treatment arm and analysis interval.

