2. SYNOPSIS

Name of Sponsor/Company: Santen Philippines Incorporated [name], [name], [name]	
Name of Investigational Product: DE-122 injectable solution	
Name of Active Ingredient: DE-122, a chimeric anti-CD105 (Endoglin) IgG1 antibody consisting of human C _κ and C _γ 1 constant regions with murine V _κ and V _h regions	
Title of Study: A Multi-Center, Randomized, Double Masked and Active Controlled Phase II Study Assessing the Efficacy, Safety of Intravitreal Injections of DE-122 in combination with Lucentis® Compared to Lucentis® Monotherapy in Subjects with Wet Age-related Macular Degeneration - AVANTE study	
Study Period: Approximately 31 months Estimated date first subject enrolled: July 2017 Estimated date last subject completed: January 2020	Phase of Development: Phase II
Primary Objective: 
 To assess the safety and efficacy of repeated intravitreal injections of DE-122 (2.0 mg/eye and 4.0 mg/eye) given in combination with Lucentis® in subjects with wet age-related macular degeneration (AMD) compared with Lucentis® alone. 	
Secondary Objective: 
 To evaluate the pharmacokinetics and immunogenicity of DE-122 following repeated IVT injections of DE-122 in subjects with wet AMD in serum samples. To evaluate biomarker candidates of DE-122 following repeated IVT injections of DE-122 in subjects with wet AMD in both serum and aqueous humor samples. 	
Methodology: This is a randomized, double masked and active controlled study assessing the safety and efficacy of repeated intravitreal injections of DE-122 (2.0 mg or 4.0 mg) in combination with Lucentis® compared to Lucentis® monotherapy in subjects with wet AMD. Approximately seventy six (76) subjects with wet AMD will be randomly assigned to one of three treatment arms:	
Arm 1: Sham + Lucentis® 0.5 mg (N=17) Arm 2: DE-122, 2.0 mg + Lucentis® 0.5 mg (N=31) Arm 3: DE-122, 4.0 mg + Lucentis® 0.5 mg (N=28)	
Subjects will receive 6 monthly intravitreal injections of DE-122 (2.0 mg or 4.0 mg) or Sham, in combination with Lucentis®. The primary analysis will be performed when all subjects complete the Week 24 visit.	

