13. PHARMACOKINETIC ASSESSMENTS

The DE-122 concentration in serum will be measured before and after Visit 1 (Day 1) and Visit 8 (Week 20) IVT administrations of DE-122 (2.0 mg and 4.0 mg) or Sham.

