23.4.17. Procedures for Pharmacokinetic Serum Sample Collection, Storage and Shipment

Approximately 5 mL of blood sample for assessment of DE-122 levels in serum will be collected pre Lucentis® injection at Visit 1 (Day 1), 3 hrs (\pm 10 mins) post DE-122 or Sham injection at Visit 1 (Day 1), Visit 2 (Day 3), Visit 3 (Week 1), Visit 4 (Week 4), pre Lucentis® injection at Visit 8 (Week 20), 3 hrs (\pm 10 mins) post DE-122 or Sham injection at Visit 8 (Week 20), Visit 9 (Week 20 + 2 days), Visit 10 (Week 20 + 7 days) and Visit 11 (Week 24) for all subjects. The actual time of dosing and sampling will be recorded on the eCRF. After each serum sample is taken from the subject, the sample is to be stored on ice until processed for the collection of the serum fraction. The blood sample should be processed for serum within approximately **1 hour** after blood collection from the subject.

There will be up to approximately 10 blood draws for PK. Approximately 5 mL or 1 teaspoon will be collected for each blood draw. The total amount of blood collected from each subject during this study will be up to approximately 50 mL.

Please refer to the separate procedure manual for sample handling, storage, and shipment.

This procedure is applicable for the subjects who have consented under the protocol prior to Version 4.0.

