## **2. STUDY OBJECTIVES AND ENDPOINTS**

### **2.1. Objectives**

The primary objective is:

- To assess the safety and efficacy of repeated intravitreal injections of DE-122 (2.0 mg per eye and 4.0 mg per eye) given in combination with Lucentis® in subjects with wet age-related macular degeneration (AMD) compared with Lucentis® alone.

The secondary objectives are

- To evaluate the pharmacokinetics and immunogenicity of DE-122 following repeated IVT injections of DE-122 in subjects with wet AMD in serum samples.
- To evaluate biomarker candidates of DE-122 following repeated IVT injections of DE-122 in subjects with wet AMD in both serum and aqueous humor samples.

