**Table 1: Schedule of Events (Continued)**

Visit Number	Visit 0 (SCRN)	Visit 1	Visit 2	Visit 3	Visit 4	Visit 5	Visit 6	Visit 7	Visit 8	Visit 9	Visit 10	Visit 11	Visit 12	Visit 13 /Exit
Visit Schedule (Time window; days)	D-14 to -1	D1	D3	W1	W4	W8	W12	W16	W20	W20 + 2 days	W20 + 7 days	W24	W28	W32
			D3	D8 (±1)	D29 (±3)	D57 (±3)	D85 (±4)	D113 (±4)	D141 (±4)	W20 + 2 days	W20 + 7(±1) days	D169 (±5)	D197 (±5)	D225 (±5)
Lucentis® IVT injection 		X			X	X	X	X	X					
DE-122 or Sham IVT Injection 		X			X	X	X	X	X					
Adverse event		X	X	X	X	X	X	X	X	X	X	X	X	X

SCRN= Screening; D=Day; W=Week; PK=Pharmacokinetic

- a. Collection and Pharmacogenomics/genomics blood sample collection.
- b. On days when either Lucentis®/DE-122 or Lucentis®/Sham IVT injections are administered, slit lamp biomicroscopy and indirect ophthalmoscopy will be performed prior to injection and within 30 minutes after DE-122 or Sham injection. This will be also applied for the post IVT injection of Rescue treatment.
- c. On days when either Lucentis®/DE-122 or Lucentis® /Sham IVT injections are administered, IOP will be performed before and after Lucentis® IVT injection. In addition, after DE-122 or Sham injection, IOP will be performed again. This will be also applied for the post injection of Rescue treatment.
- d. Selected sites will conduct.
- e. Serum and urine pregnancy tests are to be performed on all females of child-bearing potential.
- f. Subjects should fast for a minimum of 8 hours prior to urine specimen and blood draw for serum chemistry tests.
- g. At baseline (Day 1, Visit 1), serum sample for DE-122 concentration (if applicable) and biomarker will be collected
- 1) prior to the Lucentis® injection;
  - 2) post DE-122 or Sham injection: 3 hours, 48 hours, 1 week and 4 weeks (prior to the Lucentis® injection).
- At Week 20, serum sample for DE-122 concentration (if applicable) and biomarker will also be collected
- 1) prior to the Lucentis® injection;
  - 2) post DE-122 or Sham injection: 3 hours, 48 hours, 1 week and 4 weeks.
- h. Pharmacogenomics/genomics blood sample can be drawn once at Day 1 or any visit after Visit 1(Day 1) during the study.
- i. Lucentis® will be administered first, and then DE-122 or Sham will be injected. Rescue treatment with any anti-VEGF IVT injection can be performed during the Week 24 and Week 28 visits.

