**Table 6: Pharmacokinetic Measures**

Pharmacokinetic Measure	Note
Area under the curve (AUC)	AUC ( $\mu\text{g/mL} \times \text{day}$ ) reflects the extent of exposure to DE-109 after injection. It equals the integral of the concentration-time curve.
$C_{max}$	$C_{max}$ denotes the peak plasma concentration of DE-109 observed after injection.
$t_{max}$	$t_{max}$ denotes the time to reach $C_{max}$ .
Elimination half-life ( $t_{1/2}$ )	$t_{1/2}$ is the time required for the concentration of DE-109 to reach half of its original value.

PK parameters will be estimated for each of the following time intervals based on plasma concentrations collected during the corresponding time interval:

- Day 1 to Week 4 visit
- Week 20 to Week 24 visit

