## 6. GENERAL CONSIDERATIONS

Besides data listings, all measures will be summarized by randomized arm and/or overall. Continuous variables will be summarized using descriptive statistics such as number of observations (n), mean, standard deviation, minimum, and maximum. Categorical variables will be tabulated using frequency (n), sometimes along with percentage (%).

All data manipulations and descriptive summaries will be implemented using SAS®, Version 9.4 or later.

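### SAP 10 summarises the Day 1 and Week 20 PK profiles separately and plans no within-subject estimate of how exposure changes with repeated dosing

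*SAP*

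**What the plan says.** SAP 2.1 sets the secondary objective: "To evaluate the pharmacokinetics and immunogenicity of DE-122 following repeated IVT injections of DE-122 in subjects with wet AMD in serum samples". The synopsis of the protocol gives the regimen: "Subjects will receive 6 monthly intravitreal injections of DE-122 (2.0 mg or 4.0 mg) or Sham".

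Protocol 13 has serum DE-122 "measured before and after Visit 1 (Day 1) and Visit 8 (Week 20) IVT administrations of DE-122". The SAP Schedule of Events, footnote g, lists pre-dose, 3 h, 48 h, 1 week and 4 weeks for Day 1, and repeats those times later: "At Week 20, serum sample for DE-122 concentration (if applicable) and biomarker will also be collected". Protocol 23.4.17 gives the total: "There will be up to approximately 10 blood draws for PK". It limits PK sampling to subjects who consented before Version 4.0 and does not say how many they are.

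SAP 4.4.2 estimates AUC, Cmax, tmax and t1/2 within two intervals. The first is "Day 1 to Week 4 visit" and the second runs from Week 20 to Week 24. SAP 10 says the parameters "will be summarized descriptively by actual treatment arm and analysis interval". SAP 6 gives the default content: "descriptive statistics such as number of observations (n), mean, standard deviation, minimum, and maximum". SAP 5.5 admits a subject to the PK Population on one DE-122 injection and one quantifiable post-injection serum value. Protocol 16.8 likewise plans only a summary after each of the two visits.

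**The concern.** Two matched profiles from one subject allow that subject's exposure after repeated dosing to be compared directly with exposure after the first injection. The planned tables do not do this. They give one row per interval, and because neither profile is required for membership, the rows can rest on different subjects. A difference between them could reflect who contributed rather than a change in exposure.

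The default statistics add a presentation problem. AUC and Cmax are usually right-skewed, so an arithmetic mean and SD describe them poorly. Post-dose tmax can take only four nominal values (3 h, 48 h, 1 week, 4 weeks), so its mean is hard to interpret.

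At stake is how well the trial answers a secondary objective from blood already drawn. No hypothesis test or sample-size figure depends on it.

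**Working it through.** **The plan's own figure.** Two profiles × five times = 10 draws, and 10 × 5 mL = 50 mL. Both agree with Protocol 23.4.17. Injections fall on Days 1, 29, 57, 85, 113 and 141, so Week 20 is the sixth scheduled injection.

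**What is absent.** SAP 2.2.4, 4.4.2 and 10 and Protocol 16.8 contain no ratio of the two intervals, no within-subject change, no trough comparison and no restriction to subjects with both profiles. By contrast, SAP 12 plans change and percent change from baseline for biomarkers, and SAP 8.1.1 plans differences with 95% intervals although no hypothesis is tested.

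**Gain from pairing.** The documents give no CV, correlation or PK sample size, so all three are assumed. Let s be the SD of log exposure in an interval, ρ the within-subject correlation and n the subjects per dose with both profiles.

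- s = √ln(1 + CV²). For CV 60%, s = √ln(1.36) = 0.554.
- Unpaired SE of the log ratio = s√(2/n).
- Paired SE = s√(2(1 − ρ)/n).
- Paired over unpaired = √(1 − ρ) = 0.84, 0.71 and 0.45 for ρ = 0.3, 0.5 and 0.8.

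The 95% interval is the ratio ×/÷ exp(t × SE), with 2n − 2 degrees of freedom unpaired and n − 1 paired. For n = 10, unpaired: exp(2.101 × 0.554 × √0.2) = 1.68. Paired at ρ = 0.5: exp(2.262 × 0.554 × √0.1) = 1.49.

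| n per dose (CV 60%) | Unpaired | Paired, ρ = 0.3 | Paired, ρ = 0.5 | Paired, ρ = 0.8 |
|---|---|---|---|---|
| 10 | 1.68 | 1.60 | 1.49 | 1.29 |
| 20 | 1.43 | 1.36 | 1.30 | 1.18 |
| 28 (all of Arm 3) | 1.35 | 1.29 | 1.24 | 1.15 |

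The unpaired column is only a benchmark, since the SAP plans no interval for any PK comparison.

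**Scale of a possible change.** Under one-compartment linear kinetics with 28-day dosing, the dose-six to dose-one ratio is (1 − r⁶)/(1 − r), where r = exp(−ln 2 × 28/t1/2). Assumed half-lives of 7, 14, 21 and 28 days give 1.07, 1.33, 1.65 and 1.97. For a ratio of 1.33 with n = 10, the unpaired interval is 1.33/1.68 to 1.33 × 1.68, or 0.79 to 2.23. Paired at ρ = 0.8 it is 1.33/1.29 to 1.33 × 1.29, or 1.03 to 1.72. At ρ = 0.3 it is 0.83 to 2.13, a small gain.

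**Summary statistics.** If exposure is log-normal, the arithmetic mean over the geometric mean is √(1 + CV²), which is √1.36 = 1.17 at CV 60%. For tmax, moving one subject of 10 from 2 to 28 days shifts the mean by (28 − 2)/10 = 2.6 days.

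**The case against.** A separate Week 20–24 summary already answers the objective as worded. A reader might infer that estimating accumulation is the purpose of the second profile, but no objective or endpoint says so. The study is exploratory, with no hypothesis and a sample size not set on statistical grounds. This stands and limits the point to an improvement.

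The list in SAP 6 is open and includes the minimum and maximum, so the range of tmax is already planned. SAP 6 also provides for data listings, so the pairs should be recoverable. Both stand, but an open list commits to nothing and a listing is not an estimate.

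A reader might infer that the missing ratio undermines the protocol's expectation of no systemic toxicity concern. It does not. Protocol 7.1.1 argues from absolute exposure against cancer subjects, most on 10 mg/kg weekly. At an assumed 50 to 80 kg, four such doses total 2,000 to 3,200 mg, or 500 to 800 times one 4 mg injection. Dividing by the highest ratio above, 1.97, leaves about 250 to 400 times. This compares doses, not measured exposure, but it shows that a sharper ratio would hardly move that argument. The planned Week 20–24 summaries bear on it directly.

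A reader might expect pairing to at least halve the standard error. That needs ρ of 0.75 or more (√0.25 = 0.5), which no document supports. Nor does the arithmetic-mean excess bias the comparison of intervals: if log variance is similar in both, it cancels in the ratio.

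Finally, a ratio may be hard to compute. Systemic exposure is expected to be low, so values below quantification are plausible. DE-122 can be withheld under the IOP rules, including at Day 1 and Week 20, with the 3 h sample then timed from Lucentis (Protocol 7.5.2.1 and 7.5.2.8). This stands, and the fix has to deal with it.

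**Conclusion.** The point holds as a minor improvement. The plan collects paired profiles and produces no within-subject estimate of the change in exposure with repeated dosing, while its two interval summaries may describe different subjects.

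The size depends on assumptions the documents cannot settle. Pairing reduces the standard error throughout the range examined, but at a correlation of 0.3 the interval narrows only from ×/÷ 1.68 to 1.60 (n = 10, CV 60%), and it reaches 1.29 only at 0.8. No stated figure is wrong and no planned decision turns on this.

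**What to change.** In SAP 10, for subjects with both profiles evaluable, add by dose:

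- the Week 20–24 over Day 1–Week 4 geometric mean ratio of Cmax and of AUC, with 95% interval and contributing n;
- the restriction of that ratio to subjects who received DE-122 at both Day 1 and Week 20, with the number of DE-122 injections received before Week 20 shown, because the sixth injection is only nominal.

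In the existing interval summaries, also report Cmax and AUC as geometric mean and geometric CV, and add the median for tmax. State in advance how concentrations below quantification are handled.

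The cost is SAP wording and one small table, with no new samples. The ratio uses a smaller subset than the PK Population and may not be estimable if most values are below quantification; in that case the table should say so and give the counts.
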